Platelet-Rich Plasma Injection for the Treatment of Stress Urinary Incontinence in Females: A Randomized Placebo-Controlled Study

Specific aims

The primary aims of this randomized controlled trial study are to:

- 1. Evaluate the efficacy of platelet-rich plasma (PRP) injection into the anterior vaginal wall for the treatment of stress urinary incontinence (SUI) compared to placebo.
- 2. Evaluate the safety of PRP injection into the anterior vaginal wall for the treatment of SUI.

Hypothesis

Anterior vaginal wall PRP injection will be safe and associated with improved SUI compared to placebo.

Research Strategy

Significance and Innovation

Stress urinary incontinence (SUI), defined by the International Continence Society as the involuntary leakage of urine on effort or exertion, or on sneezing or coughing [1], is estimated to affect up to 49% of women [2, 3], many of whom undergo an operative intervention. Conservative management for SUI includes lifestyle interventions, pelvic floor muscle training, and incontinence pessaries. If conservative treatment fails or is not desired, surgical treatment via midurethral sling, colposuspension, pubovaginal sling, or bulking agent may be considered. Although surgery is highly effective in curing SUI, there are significant risks, such as hemorrhage, visceral injury, voiding dysfunction, chronic pain, and mesh exposure. Specifically, mid-urethral sling-related complications have been reported in up to 6% of patients [4] and include pain, exposure, erosion, dyspareunia, and long-term disability [5]. Complications after urethral bulking can include abscess formation, delayed hypersensitivity reactions, and vaginal erosion [6]. Fascial slings, compared to mid-urethral slings, have been shown to have a higher incidence of voiding dysfunction sometimes requiring intermittent catheterization, urethrolysis and/or prolonged suprapubic catheter use [7]. **Thus, there is an urgent need to evaluate innovative, minimally invasive, and low-risk procedures for SUI**.

Platelet-rich plasma (PRP) is an autologous solution of human plasma with a high concentration of platelets. Platelet-rich plasma contains various growth factors that enhance the healing process and regeneration by initiating the stages of cell proliferation, differentiation, angiogenesis, and chemotaxis. The rationale for use and therapeutic potential of a high concentration of platelets is based on their capacity to supply supraphysiologic amounts of essential growth factors and cytokines which then provide a regenerative stimulus, promoting tissue repair [8]. Important growth factors released from platelets during the healing process include platelet-derived growth factor (PDGF), transforming growth factor (TGF- β), vascular endothelial growth factor (VEGF), epidermal growth factor (EGF), basic fibroblast growth factor (bFGF), and insulin-like growth factor (IGF-1) [9].

PRP has been described for the treatment of various health conditions, from hair loss to joint injuries. PRP is most studied and used for the treatment of musculoskeletal soft tissue injuries, including tendinopathies and tendon tears, and ligament, muscle, and cartilage injuries [10]. The injection of PRP is not a new technology, but it has not been well-studied in the field of urogynecology. Two small series have reported on use of PRP

for the treatment of female SUI, suggesting successful treatment outcomes in up to 80% of patients [11] [12]. With this study, we will provide higher quality evidence on the use of PRP in the treatment of SUI.

This study will aim to determine the 6-month post-treatment efficacy of PRP injection in the treatment of **SUI.** Knowledge gained from this study has the power to change clinical practice by equipping physicians with a minimally invasive and likely low risk SUI treatment.

Approach

The primary aims of this study are to determine the efficacy and safety of PRP injection into the anterior vaginal wall for the treatment of SUI.

The primary efficacy aim will be determined by the following outcome measures:

- 1. Negative urinary stress test (no leakage noted on examination during cough or Valsalva maneuvers at a standardized bladder volume of 300 mL [13]
- 2. Subjective outcome with improvement in the Patient Global Impression of Improvement (PGI-I), with positive response defined as "very much better" (1) or "much better" (2). [14]

Treatment "success" will be defined as a negative CST and a reported PGI-I of "very much better" or "much better" 6 months after treatment.

The primary safety aim will be assessed by monitoring adverse events classified by the Clavien-Dindo Classification.

Secondary Outcomes that will be compared between groups include:

- 1. Female Sexual Function Index (FSFI) scores
- 2. Incontinence-Quality of Life (I-QOL) scores
- 3. Perception of Monetary Value
- 4. Questionnaire for Urinary Incontinence Diagnosis (QUID)
- 5. Visual Analog Scale (VAS) for patient pain/discomfort
- 6. Visual Analog Scale (VAS) for procedure difficulty (by provider)

Eligibility Criteria

- 1. Women aged 18 years or older
- 2. Pure or stress-predominant urinary incontinence with the Medical, Epidemiologic, and Social Aspects of Aging questionnaire (MESA) stress incontinence symptom score greater than MESA urge incontinence symptom score
- 3. Observation of leakage by provocative stress test at bladder volume \leq 300 mL [15]
- 4. Post void residual < 150 mL

Exclusion criteria

- 1. Currently pregnant or trying to conceive
- 2. Currently breastfeeding
- 3. Interstitial cystitis

- 4. Urgency urinary incontinence predominance or currently being treated for overactive bladder with medication, percutaneous tibial nerve stimulation, bladder chemodenervation, or sacral neuromodulation
- 5. Currently being treated for a sexually transmitted disease
- 6. Pelvic organ prolapse greater than stage 2 according to the Pelvic Organ Prolapse Quantification System
- 7. Periurethral mass
- 8. Active gynecologic, urologic or colorectal cancer
- 9. Any history of cancer within the last 5 years
- 10. Mental disorder making the patient unable to provide consent
- 11. Undiagnosed abnormal uterine bleeding
- 12. Genitourinary fistula
- 13. Prior SUI surgery
- 14. Use of anti-platelet or anti-coagulant medication
- 15. Use of non-steroidal anti-inflammatories
- 16. Regular use of non-steroidal anti-inflammatories

Methodology

This is a single-blind prospective randomized controlled trial comparing the efficacy of injection of 5 mL PRP into the anterior vaginal wall versus injection of 5 mL injectable saline for the treatment of SUI in females.

The study population is women aged 18 years or older with stress-predominant urinary incontinence conformed by a positive cough stress test, as well as a higher SUI MESA score over the UUI MESA score. The approximate number of subjects will be 50, based on a power analysis as described below. The length of follow up will be 6 months post injection.

Following approval by the local Institutional Review Board (IRB), subjects will be recruited from the University of Iowa Hospitals and Clinics Urology and Urogynecology Clinics during regularly scheduled appointments. Subjects will be referred to the study by physician referral. This trial will be registered with clinicaltrials.gov prior to any subject enrollment.

Enrollment

Potential participants will be approached in clinic and be given an overview of the study. If they meet the inclusion criteria and none of the exclusion criteria, the research coordinator will initiate the informed consent process. To assure patient privacy during the informed consent process, the discussion will be held in a private room at the clinic, with the door closed. Once the potential participant has ample time to consider the study, they will be asked to sign the written consent form with the consent provider. A copy of the signed consent form will be given to the patient and the original placed in the research record.

Equipment

Using the Arthrex Autologous Conditioned Plasma (ACP) Double Syringe System (Arthrex Inc, Naples, Florida), approximately 15 mL of the subject's venous blood will be collected from the antecubital fossa. The sample, in the ACP system, will be centrifuged in the clinic lab space. A representative from the company may be present for this portion of the procedure to ensure proper use of the centrifuge. However, the company is not funding this study, has not been involved with protocol development and will not be involved in data analysis,

interpretation or publication of results. Centrifuging takes approximately 5 minutes. At the end of the process, approximately 5 mL of the subject's PRP will be separated. The principal investigator (PI) and research staff will be trained on the processing procedure by [name] from the Sport Medicine Clinic and by the company representative, in order to ensure the procedure is performed using standardized and safe methods.

Randomization

Randomization will be performed with the help of a biostatistician. Participants will be block randomized with equal allocation to the treatment and control groups. To develop the assignment table, blocks of size 2, 4, or 6 participants were randomly selected until we achieved the anticipated sample of 50. Within each block, half of participants will be randomly assigned to one group and half to the other, ensuring equal treatment allocation. The randomization schedule will be transferred to sequentially numbered, opaque, sealed envelopes.

The principal investigator and the research coordinator will be responsible for maintaining the confidentiality and security of the randomization.

At this point, the clinical research coordinator will then open the randomization envelope. Randomization will be performed as described. The subject's initials and the date of injection will be written on the outside of the envelope prior to the envelope being opened. This writing will be transferred to the card containing the assigned randomization inside the envelope with carbon transfer paper. If the subject is assigned the active treatment, the sample will be used. If the subject is assigned the placebo, the sample will be discarded appropriately.

Injection Procedure

The injection procedure will be performed using previously published methods. The PI and 1 co-investigator will perform the procedure to ensure it is done in a standardized and reproducible method throughout the trial.

The injector will enter the clinic room with the patient already in the dorsal lithotomy position. A local anesthetic of lidocaine gel 2% will have been applied to the distal anterior vaginal wall 20 minutes before injections. The injector will then inject 5 mL total of either the active PRP or the placebo based on

randomization. The PRP will be injected into 3 sites of the anterior vaginal mucosa at the mid-urethra (about 1 cm proximal to the urethral meatus) using a 30-gauge needle. *Figure 1* diagrams the location and depth of the injections. The location of the injections is based on a pilot study by Long *et al* [12]. Immediately after the procedure, the patient will be given the VAS for pain/discomfort related to the procedure and the injector will complete the VAS for procedure difficulty.

At baseline and at time points of 1 month, 3 months, and 6 months, subjects will complete the previously described validated questionnaires (see visit details below). At a 1-month telephone visit, a subset of the questionnaires will be administered, and patients will be queried about any adverse events. At baseline and at time points of 3 and 6 months, all validated questionnaires will be completed, as well as a pelvic exam with a urinary stress test, performed by a nurse practitioner specifically trained in urogynecology, and who did not perform the injections and thus blinded to the randomization. All adverse events will be recorded and classified per the Clavien-Dindo Classification.

Figure 1. Location and Depth of Injections¹²

At the end of the 6 months, subjects will be unblinded.

If subjects have symptoms of SUI which are refractory to treatment with PRP they will be referred to Urology or Urogynecology and will be offered standard of care following completion of the final study visit. If patients wish to receive alternative treatment for SUI prior to completion of 6-month follow-up they will be exited from the trial and final outcomes will be assessed at that time

Subjects will be provided a \$50 eVoucher upon completion of the 6-month follow-up visit.

Data will be stored in a secure REDCap database, only accessible to the research team members. Randomization envelopes and the Randomization Log will be kept in a locked cabinet.

Power Analysis

Sample size calculations were performed based on a desired power of at least 90% and assuming true response rates of 70% and 20% for treatment and placebo groups, respectively. The 70% response rate in the active PRP treatment group was chosen based on prior studies of PRP, as well as urethral bulking procedures [12] [16] [17]. The response rate of 20% in the placebo arm was chosen based on prior urethral bulking studies showing a 20% rate of negative CST after placebo [18]. Using an unadjusted alpha of 0.05, a sample of 38 subjects (19 per treatment group) is the minimum number required to have >90% power to detect a difference between the response rates of the two treatments.

In order to account for a 20% drop-out rate, we will plan to enroll a total of 50 patients (25 per treatment group).

Statistical Analysis and Data Reporting

For this study we will assess the demographics of our patients by providing summary statistics stratified by treatment group. Comparisons between the demographics of the two treatment groups will be made using Fisher's Exact or chi squared tests for categorical variables and using T-test or Wilcoxon rank sum tests for continuous variables, where appropriate. Primary and secondary outcomes will also be compared using treatment-stratified summary statistics, and p-values obtained using the aforementioned statistical tests.

Univariate logistic regression models will be fit using the demographic variables obtained in the study, as well as treatment, to predict patients' primary outcomes. Then, one multivariate model will be constructed for each primary outcome with treatment included as a predictor and an AIC-based stepwise forward model selection procedure dictating what other variables to include into the model. Univariate generalized linear models using treatment group as the predictor variable will also be examined for the secondary outcomes.

Data will be reported using the CONsolidated Standards Of Reporting Trials (CONSORT) guidelines and standard flow diagram.

Breaking the Blind

A subject's treatment assignment will not be broken until the end of the study unless medical treatment of the subject is dependent on knowing the treatment the subject received. Should a medical emergency require the blind to be broken the investigator may unblind an individual subject's treatment allocation.

Research Visit Summary:

Baseline visit confirming eligibility with inclusion and exclusion criteria

Basic demographic data will be recorded

Past medical history will be recorded

Pregnancy test (if of child-bearing age)

Urinalysis dipstick to exclude active urinary tract infection

Bladder scan to see how much urine is in the bladder prior to urinary stress test

Pelvic exam with urinary stress test

Bladder scan after voiding to check post-void residual

Three surveys before the procedure

- Female Sexual Function Index
- Incontinence Quality of Life
- Questionnaire for Urinary Incontinence Diagnosis

Blood draw of about 15 mL

Randomization

Injection procedure

Visual analog Scale (VAS) for pain/discomfort associated with the procedure Injector completes Visual analog Scale (VAS) for level of difficulty of procedure

1-Month Telephone Visit

Record any adverse events

Surveys

- Incontinence Quality of Life
- Questionnaire for Urinary Incontinence Diagnosis
- Patient Global Impression of Improvement

3-Month Visit

Record any adverse events Pelvic exam with cough stress test Surveys

- Female Sexual Function Index
- Incontinence Quality of Life
- Questionnaire for Urinary Incontinence Diagnosis
- Patient Global Impression of Improvement

6-Month Visit

Record any adverse events Pelvic exam with cough stress test Surveys

- Female Sexual Function Index
- Incontinence Quality of Life
- Questionnaire for Urinary Incontinence Diagnosis
- Patient Global Impression of Improvement
- Perception of Monetary Value

\$50 eVoucher for completion of 6-month follow-up visit

Benchmarks for Success

After enrollment of the first 5 subjects, a quality control of the data collected and entry will be performed. Additional quality control will be performed by the PI after every 10 patients. Meticulous recording of adverse events will be performed. If adverse events are frequent and distressing, the project will be halted and data collected to that point will be analyzed.

After enrollment of 25 subjects, preliminary data and adverse events will be analyzed by a Data and Safety Monitoring Board made up of the research team members.

Potential Problems

Potential problems include low or slow enrollment. In addition to screening patients in the clinic, we can also plan on advertising the study via the University of Iowa listserv and/or advertisement materials to other clinics, such a family medicine, internal medicine, and gynecology.

Since this is a new procedure not well-described in the literature, another potential problem may be the learning curve of the procedure. To mitigate this, only two clinicians will serve as the injector, including the PI

and one other fellowship-trained FPMRS specialist. This will allow consistent and standardized procedure methods.

Timetable and Plan For Completing Project

February 2022: set up REDCap database

March 2022: complete IRB application (as of grant submission, the IRB application has been approved pending minor modifications)

June 2022: start screening clinics for eligible patients, enroll subjects

June 2022 - September 2023: enroll patients, collect data

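### A woman who misses the 6-month visit has no 6-month outcome as the plan is written, although a telephone PGI-I could establish failure without an examination

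*Combined protocol and SAP*

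**What the plan says.** The Approach section sets the endpoint: "Treatment 'success' will be defined as a negative CST and a reported PGI-I of" followed by "very much better' or 'much better' 6 months after treatment". The list of efficacy measures just before it gives the PGI-I rule: "with positive response defined as 'very much better' (1) or 'much better' (2".

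The follow-up paragraphs under Injection Procedure say: "At a 1-month telephone visit, a subset of the questionnaires will be administered". The Research Visit Summary shows that this subset includes the PGI-I. At 6 months the PGI-I appears only in the clinic visit list, beside the pelvic examination and stress test. No alternative is given for a woman who does not come. Both measures are also taken at 3 months, but no rule carries them forward.

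The plan makes three provisions that bear on loss:

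- Power Analysis: "In order to account for a 20% drop-out rate, we will plan to enroll a total of 50 patients".
- The follow-up paragraphs: women who want another treatment for stress incontinence before 6 months leave the trial and have their outcomes taken when they leave.
- A $50 voucher for completing the 6-month visit.

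Statistical Analysis and Data Reporting names Fisher's exact or chi-squared tests. It gives no analysis set and no rule for missing outcomes. Participants are unblinded at the end of the 6 months.

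**The concern.** Success needs two conditions, so one unfavourable answer is enough to establish failure. For a non-attender, a short call could therefore turn a missing outcome into an observed failure. The plan already uses the telephone for this instrument at 1 month but not at 6 months, when it counts.

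Over-enrolment protects the number of evaluable women. It does not protect against bias if the women who fail to return are mainly those who did not improve. In that case the success rate among attenders is too high in each arm, and unequal loss can distort the comparison.

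The information also cannot be properly recovered later. Once women know their assignment, the PGI-I becomes an unblinded subjective answer.

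**Working it through.** **Inputs.** Power Analysis gives the rates: "assuming true response rates of 70% and 20% for treatment and placebo groups, respectively". It also gives 25 enrolled per arm and 20% drop-out, which is 10 women in all. The documents give no reasons for drop-out, so who is lost is an assumption throughout. Expected counts per arm are 17.5 successes and 7.5 failures on PRP, and 5 successes and 20 failures on placebo.

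**The plan's own figure.** "Using an unadjusted alpha of 0.05, a sample of 38 subjects (19 per treatment group) is the minimum number required". The two-sided, pooled-variance formula for two proportions gives

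n = [1.96·√(2·0.45·0.55) + 1.2816·√(0.7·0.3 + 0.2·0.8)]² / 0.5² = 18.6,

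so 19 per arm and 38 in total. Power is 90.6% at 19 per arm and 88.9% at 18. The 38 reproduces. For enrolment, 38/0.8 = 47.5, or 48, while the timetable's base of 40 gives 40/0.8 = 50. The sample size is sound.

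**Effect of losing failures.** The completer rate is successes/(25 − lost). The true difference is 50 points in the first four rows and 0 in the last two.

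| Failures lost (PRP, placebo) | PRP | Placebo | Difference (points) |
|---|---|---|---|
| 5, 5 | 17.5/20 = 87.5% | 5/20 = 25.0% | 62.5 |
| 2.73, 7.27 (equal rate among failures, 10/27.5 = 36.4%) | 17.5/22.27 = 78.6% | 5/17.73 = 28.2% | 50.4 |
| 5, 0 | 17.5/20 = 87.5% | 5/25 = 20.0% | 67.5 |
| 0, 5 | 17.5/25 = 70.0% | 5/20 = 25.0% | 45.0 |
| No true effect (20% in both arms): 5, 5 | 5/20 = 25.0% | 5/20 = 25.0% | 0 |
| No true effect: 8, 2 | 5/17 = 29.4% | 5/23 = 21.7% | 7.7 |

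The rate rises in any arm that loses failures. The difference has no fixed direction.

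**What the call adds if loss is random.** Five are lost per arm: 3.5 successes and 1.5 failures on PRP, 1 success and 4 failures on placebo. Attenders show 14/20 and 4/20, which is unbiased at 50 points. The best/worst-case limits give the unresolved women opposite outcomes in the two arms:

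- No call: 14/25 − 9/25 = 20 to 19/25 − 4/25 = 60 points (width 40).
- Call settles every lost failure: 14/25 − 5/25 = 36 to 17.5/25 − 4/25 = 54 points (width 18).
- Call settles half of them (0.75 on PRP, 2 on placebo): 14/25 − 7/25 = 28 to 18.25/25 − 4/25 = 57 points (width 29).

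Giving the unresolved women the same outcome in both arms yields 14/25 − 4/25 = 40 and 17.5/25 − 5/25 = 50. That pair does not bound the difference, so opposite directions are needed.

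**How to treat unresolved women.** The call settles failures only. Adding them and dropping the unresolved women gives 14/21.5 − 4/24 = 65.1% − 16.7% = 48.4 points, a downward skew of 1.6. Counting unresolved women as not successes gives 56% against 16%, or 40 points, if loss is random. It gives 70% against 20%, or 50 points, if those lost are all failures. At 56% against 16% with 25 per arm, power is about 86% (normal approximation), 88% (chi-squared, exact enumeration) or 80% (Fisher).

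**The case against.** A reader might infer that the trial will overstate the PRP effect by 12.5 points (62.5 − 50). The documents do not support that. The figure needs 5 failures lost in each arm, which is 5/7.5 = 67% of PRP failures but 5/20 = 25% of placebo failures. Participants are blinded until 6 months, and nothing in the plan suggests why a failing woman on PRP should be 2.7 times as likely to disappear. With equal loss rates among failures the bias is 0.4 points, and each arm's rate rises by about the same amount (8.6 and 8.2 points).

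A reader might also infer that the plan prescribes a completer analysis, or that extra enrolment is its only answer to loss. Neither is right. No analysis set is named, and the exit assessment covers women leaving for other treatment, who are probably among the clearest non-responders. The voucher also encourages attendance.

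Two practical limits stand. Some women will not be reached, and a failure that would show only on the stress test stays unresolved. In addition, if unresolved women are counted as not successes, the primary estimate is the same with or without the call, because every untested non-attender counts as not a success either way. The call replaces part of that assumption with observation, narrows the limits and nearly completes the PGI-I as a separate measure.

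What remains is that plain no-shows and other withdrawals have no 6-month outcome, no rule says how they count, and no rule says how an exit result enters the 6-month endpoint.

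**Conclusion.** The concern holds as a gap in data collection and in the analysis rule, not as a demonstrated bias in the treatment effect. Because the endpoint requires both components, a PGI-I outside the top two categories is sufficient evidence of failure, and the plan does not collect it from a woman who misses the 6-month visit.

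If failures are the ones lost, completer rates are too high. On the plan's rates with 10 failures lost, the difference is 62.5 points at 5 per arm and 50.4 at equal loss rates, against a true 50. It can also fall below 50, as the 45 points with loss of 5 from placebo only shows. With no true effect and equal loss there is no spurious difference.

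The firmest gain is in the limits under random loss: 36 to 54 points instead of 20 to 60, or 28 to 57 if half the lost failures are settled. The 36 to 54 assumes that every lost failure is reached and gives an unfavourable PGI-I. All these figures rest on the planned 20% loss and the assumed 70% and 20%. The change is cheap and worth making, and it must be made before women are unblinded.

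**What to change.** 1. In the 6-Month Visit list, add that if a woman does not attend, the blinded nurse practitioner takes the PGI-I by telephone at 6 months, before unblinding. Any answer other than 1 or 2 is scored as not a success.
2. In Statistical Analysis and Data Reporting, keep all randomised women in the primary comparison. In the single primary test, count as not successes those still unresolved, meaning a PGI-I of 1 or 2 without a stress test, or not reached.
3. Report best/worst-case limits that assign unresolved women opposite outcomes in the two arms.
4. State how an assessment made at early exit enters the 6-month endpoint.

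**Cost.** About 10 short calls (20% of 50) and a few lines of text, with no extra patients or procedures. A few women give the PGI-I by a different mode. Counting unresolved women as not successes dilutes the estimate to 40 points against 50 if loss is random, with power of about 80% (Fisher) to 88% (chi-squared) at 25 per arm. The sponsor should accept that loss knowingly or revisit the enrolment figure.

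### Safety is a primary aim, but no adverse-event entry is scheduled on injection day and none is solicited until the 1-month call, so mild early events are likely to be under-counted in both arms

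*Combined protocol and SAP*

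**What the plan says.** Specific aims lists safety beside efficacy as a primary aim, and the Approach section fixes the endpoint: "The primary safety aim will be assessed by monitoring adverse events classified by the Clavien-Dindo Classification".

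The follow-up paragraphs under Injection Procedure place the first patient query at one month: "At a 1-month telephone visit, a subset of the questionnaires will be administered, and patients will be queried about any adverse events". The Research Visit Summary agrees. The line "Record any adverse events" first appears under the 1-month telephone visit. The 3- and 6-month lists carry it too ("Record any adverse events Pelvic exam with cough stress test Surveys").

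The baseline list, which includes randomization and injection, has no such line. After the injection it holds only the patient's pain/discomfort VAS and a final item for the operator: "Injector completes Visual analog Scale (VAS) for level of difficulty of procedure".

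Two sentences, one under Injection Procedure and one under Benchmarks for Success, promise in general terms that adverse events will be fully and carefully recorded. Neither says when or by what means events in the first month are to be collected.

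**The concern.** A safety rate depends on when and how events are asked about. Non-serious events in the days after a needle procedure are easily forgotten or not thought worth mentioning a month later. It is a reasonable inference, though not something the documents state, that harms of a single injection session fall mainly in those days. If so, the period with most to report has no scheduled question in it.

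What is at stake is the absolute event rate by Clavien-Dindo grade, especially the mild grades. The plan hypothesizes that PRP is safe and describes the procedure as new. With 25 women per arm, losing a few mild events could change a reported rate noticeably or produce an arm with no events at all. That error would favor the trial's own hypothesis.

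**Working it through.** **Schedule check.** The adverse-event content of each visit list in the Research Visit Summary, set side by side:

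| Visit | Adverse-event line | Other record of harm |
|---|---|---|
| Baseline and injection | No | Pain/discomfort VAS, just after the procedure |
| 1 month, telephone | Yes | None |
| 3 months, clinic | Yes | Pelvic exam |
| 6 months, clinic | Yes | Pelvic exam |

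Three of three follow-up lists carry the line; the injection list does not. The narrative text describes no contact between injection and the 1-month call. The interval without a scheduled query is therefore about one month. The pain VAS is a secondary outcome in the Approach section and is not part of the graded adverse-event endpoint.

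**Illustration of size.** The plan gives no expected event rate and no estimate of recall, so there is no figure of its own to reproduce. The inputs are:

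- n = 25 PRP women (Power Analysis), all assumed to be followed.
- p = true risk of an early event per woman. Assumed.
- c = share of those events that reach the record by any route. Assumed.

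Recorded rate = p × c. Chance that none is recorded = (1 − p × c)^25.

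At p = 10%:

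- c = 100%: recorded rate 10%; 0.90^25 = 7.2%.
- c = 90%: recorded rate 9%; 0.91^25 = 9.5%.
- c = 50%: recorded rate 5%; 0.95^25 = 27.7%.

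Chance of recording no event, over a wider range of assumptions:

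| True risk p | c = 100% | c = 75% | c = 50% |
|---|---|---|---|
| 5% | 27.7% | 38.5% | 53.1% |
| 10% | 7.2% | 14.2% | 27.7% |
| 20% | 0.4% | 1.7% | 7.2% |

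**Effect on the comparison between arms.** If c is the same in both arms, the recorded difference is c × (p1 − p2), which shrinks. The recorded ratio is (c × p1)/(c × p2) = p1/p2, which does not change. The distortion is then in the absolute rates and their difference, not in the relative risk.

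**The case against.** The strongest reply is that a missing checklist line is not a missing duty. The injector is in the room, the woman completes a pain score immediately afterward, and staff are bound by the general promise to record all adverse events. The Breaking the Blind section provides for medical emergencies, so the plan expects some safety information outside the scheduled visits. Contact instructions may also have stood on consent pages that are not available here, so the absence of a stated reporting route cannot be held against the plan. All of this stands. It narrows the point to non-serious events after the woman leaves the clinic, for which a general promise supplies no collection point.

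The illustration also rests on assumed inputs. That is true, and it shows direction and possible range only.

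Four stronger readings are tempting and are not supported:

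- *The whole safety aim rests on month-old recall.* It does not. Events on the day can be recorded by staff, and procedural pain is scored at once.
- *The halting rule runs only on late information.* The rule reads "If adverse events are frequent and distressing, the project will be halted". It is tied to the events themselves, not to a scheduled query.
- *Early harms are established as the most likely.* This is a sensible inference, but the documents do not say it.
- *Bladder scans are missing at 3 and 6 months.* The plan lists "Bladder scan after voiding to check post-void residual" at baseline only. It names voiding dysfunction as a risk of surgery ("there are significant risks, such as hemorrhage, visceral injury, voiding dysfunction, chronic pain, and mesh exposure"), not of PRP. Scans that late could not detect transient early difficulty in any case.

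**Conclusion.** The point holds in a limited form. Followed as written, the schedule leaves non-serious events after the clinic stay unsolicited for about a month, in a trial where safety is a primary aim. Mild early events are likely to be under-counted in both arms and absolute rates understated.

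This conclusion rests on two assumptions: that some mild events occur early, and that some of them are neither volunteered nor recalled at one month. Both are plausible; neither can be quantified from the documents. Relative rates need not be distorted if capture is equal between arms. The case for acting is that ascertainment for a primary aim can be improved at small cost, not that the safety result would be invalid without the change.

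**What to change.** Make two changes, identical in both arms:

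1. Add the line "Record any adverse events" to the injection-visit list, after the injection and before the woman leaves the clinic.
2. Add a short, automated, patient-completed adverse-event form in REDCap at about day 7, with existing research staff reviewing the returns. The follow-up text now restricts database access to the research team, so adjust it to allow patient entry through the form.

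The cost is one line in the schedule, one form to build, one more brief contact per woman and some review time for existing staff. No new procedure is needed. The recorded event rate will probably be slightly higher, which should be expected when the results are read.
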